8.4 Informed consent

The Investigator or designee will:

- Ensure each volunteer is given full and adequate oral and written information about the nature, purpose, possible risk, and benefit of the study
- Ensure each volunteer is notified that they are free to discontinue from the study at any time
- Ensure that each volunteer is given the opportunity to ask questions and allowed time to consider the information provided
- Ensure each volunteer provides signed and dated informed consent(s) before conducting any procedure specifically for the study
- Ensure the original, signed informed consent form(s) is/are stored in the Investigator's Study File
- Ensure a copy of the signed informed consent form(s) is/are given to the volunteer
- Ensure that any incentives for volunteers who participate in the study as well as any provisions for volunteers harmed as a consequence of study participation are described in the informed consent form(s) that is/are approved by an ethics committee

If any new information on the study medication becomes available which may influence the decision of the volunteer to continue the study, the Investigator should inform the volunteer of such information immediately, record this in a written form, and confirm with the volunteer if he wishes to continue the participation in the study. In addition, if the Investigator deems it necessary to revise the informed consent form(s), they should revise it immediately (refer to Section 8.5). The Investigator should re-explain to the volunteers using updated informed consent form(s) even if the volunteers have already been informed of the new information verbally. Written informed consent to continue participation in the study should be provided separately.

8.5 Changes to the protocol and informed consent form

Study procedures will not be changed without the mutual agreement of the Investigator and AstraZeneca.

If there are any substantial changes to the CSP, these changes will be documented in a CSP amendment and, where required, in a new version of the CSP (revised CSP).

The amendment is to be approved by the relevant ethics committee and, if applicable, also the national regulatory authority approval before implementation. Local requirements are to be followed for revised CSPs.

AstraZeneca will distribute any subsequent amendments and new versions of the CSP to the Investigator. For distribution to ethics committee see Section 8.3.

If a CSP amendment requires a change to the study center's informed consent form(s), AstraZeneca and the study center's ethics committee are to approve the revised informed consent form(s) before the revised form is used.

If local regulations require, any administrative change will be communicated to or approved by each ethics committee.

8.6 Audits and inspections

Authorized representatives of AstraZeneca, a regulatory authority, or an ethics committee may perform audits or inspections at the study center, including source data verification. The purpose of an audit or inspection is to systematically and independently examine all study-related activities and documents, to determine whether these activities were conducted, and data were recorded, analyzed, and accurately reported according to the CSP, GCP, guidelines of the ICH, and any applicable regulatory requirements. The Investigator will contact AstraZeneca immediately if contacted by a regulatory agency about an inspection at the study center.

9. STUDY MANAGEMENT

will manage the study on behalf of AstraZeneca.

9.1 Prestudy activities

Before the first volunteer is entered into the study, it is necessary for a representative of AstraZeneca to visit the study center to:

- Determine the adequacy of the facilities
- Determine availability of appropriate volunteers for the study
- Discuss with the Investigator (and other personnel involved with the study) their responsibilities with regard to CSP adherence, and the responsibilities of AstraZeneca or its representatives. This will be documented in a CSA between AstraZeneca and the Investigator.

9.2 Training of study site personnel

Before the first volunteer is entered into the study, an AstraZeneca representative will review and discuss the requirements of the CSP and related documents with the investigational staff and also train them in any study-specific procedures and system(s) utilized.

The Investigator will ensure that appropriate training relevant to the study is given to all of these staff, and that any new information relevant to the performance of this study is forwarded to the staff involved.

The Investigator will maintain a record of all individuals involved in the study (medical, nursing, and other staff).

9.3 Monitoring of the study

During the study, an AstraZeneca representative will have regular contacts with the study center, including visits to:

- Provide information and support to the Investigator
- Confirm that facilities remain acceptable
- Confirm that the investigational team is adhering to the CSP, that data are being accurately and timely recorded in the eCRFs, that biological samples are handled in accordance with the Laboratory Manual, and that study drug accountability checks are being performed
- Perform source data verification (a comparison of the data in the eCRFs with the volunteer's medical records at the hospital or practice, and other records relevant to the study) including verification of informed consent of participating volunteers. This will require direct access to all original records for each volunteer (eg, clinic charts).

- Ensure withdrawal of informed consent to the use of the volunteer's biological samples is reported and biological samples are identified and disposed of/destroyed accordingly, and the action is documented, and reported to the volunteer

The AstraZeneca representative will be available between visits if the Investigator or other staff at the study center needs information and advice about the study conduct.

Source data

Refer to the CSA for location of source data.

9.4 Study agreements

The Investigator at the study center should comply with all the terms, conditions, and obligations of the CSA, or equivalent, for this study. In the event of any inconsistency between this CSP and the CSA, the terms of CSP shall prevail with respect to the conduct of the study and the treatment of volunteers and in all other respects, not relating to study conduct or treatment of volunteers the terms of the CSA shall prevail.

Agreements between AstraZeneca and the Investigator should be in place before any study-related procedures can take place, or volunteers are enrolled.

Archiving of study documents

The Investigator follows the principles outlined in the CSA.

9.5 Study timetable and end of study

The end of the study is defined as 'the last visit of the last volunteer undergoing the study'.

The study is expected to start in Quarter 2, 2012 and to end by Quarter 3, 2012.

The study may be terminated at the study center if the study procedures are not being performed according to GCP or if recruitment is slow. AstraZeneca may also terminate the entire study prematurely if concerns for safety arise within this study or in any other study with AZD6244.

10. DATA MANAGEMENT

Data management will be performed by _____.

A 21 Code of Federal Regulations part e used for this study. Electronic CRFs will be produced by _____ for each volunteer.

The data collected through third party sources will be obtained and reconciled against study data.

Adverse events and medical/surgical history will be classified according to the terminology of the latest version the Medical Dictionary for Regulatory Activities (MedDRA). Medications

will be classified according to the AstraZeneca Drug Dictionary. All coding will be

Data queries will be raised for inconsistent, impossible, or missing data. All entries to the study database will be available in an audit trail.

The data will be validated as defined in the Data Management Plan. Quality control procedures will be applied to each stage of data handling to ensure that all data are reliable and have been processed correctly.

When all data have been coded, validated, and locked, a clean file will be declared. Any treatment-revealing data may thereafter be added and the final database will be locked.

Data associated with biological samples will be transferred to laboratories internal or external to AstraZeneca.

11. EVALUATION AND CALCULATION OF VARIABLES

11.1 Calculation or derivation of safety variable(s)

11.1.1 Calculation of change from baseline

Change-from-baseline variables will be calculated for the safety variables listed below, as the posttreatment value minus the value at baseline. The baseline values will be as follows:

- Clinical laboratory tests: Day -1 in corresponding treatment period
- Vital signs: Day 1, predose in corresponding treatment period
- Digital ECG: Day 1, predose in corresponding treatment period

If a volunteer is missing the baseline collection, the previous nonmissing evaluation will become the baseline value. If no baseline or previous-to-baseline evaluations exist, then the baseline value will be treated as missing and no change-from-baseline value will be calculated.

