1.3.3 Safety monitoring

Hematology, clinical chemistry (including troponin, brain natriuretic peptide [BNP], creatine kinase myocardial band [CK-MB], and total creatine phosphokinase [CPK]), and urinalysis will be taken. Telemetry and paper printout ECGs (pECGs) for immediate safety assessment as well as digital ECGs (dECGs) for pharmacodynamic assessments will be performed. Baseline and as needed eye examination will be performed. Blood pressure and pulse will be recorded. Echocardiograms will be performed (BNP, troponin, CPK, and CK-MB blood draw will be performed on the same day as the echocardiograms). Collection of AE reports throughout the study will also be monitored.

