Prior/concomitant medications	X	X	X	X	X
Physical examination ^d	X	X		X	X
Eye examination ^e	X				
Laboratory assessments (clinical chemistry, hematology, and urinalysis ^f)	X ^g	X			X
Cardiac biomarkers ^{h,n}	X	X	X		X
Drug screening	X	X			

Table 2 Study plan

Assessment	Screening	Dosing Periods 1, 2, 3, and 4 ^a			Follow-up
Visit	1		2, 3, 4, and 5		6
Days Assessment	Day -28 to -2	-1	1	2	At least 7 days after the last dose
Vital signs (including blood pressure and pulse rate) ^k	X	X	X ^j	X	X
12-lead dECG ^k			X ^l	X	
12-lead pECG	X	X	X ^l	X	X
Telemetry ^m		X ^r	X		
Echocardiogram ⁿ	X	X			X
Randomization			X ^o		
Dose administration			X ^p		
PK blood sampling ^q			X	X	
Optional pharmacogenetic sampling			X ^r		
SAE recording	X	X	X	X	X
AE recording		X	X	X	X
Discharge				X	

^a At least 7-day washout period will occur between each AZD6244 administration.

^b Informed consent will be collected prior to any study-specific procedures being performed.

^c Pharmacogenetic informed consent is required if the subject volunteers for the pharmacogenetic blood sampling. Period 1, Day 1 only.

^d Complete physical examinations will be performed at screening and at follow-up. A brief physical examination will occur on Day -1 and discharge of each treatment.

^e Ophthalmological examination will be performed any time prior to the first dose of IP and on any occurrence of a visual AE.

^f Microscopy will be performed if abnormal urinalysis results.

^g Subjects will fast for 4 hours prior to clinical laboratory evaluations at screening. Creatinine clearance will be estimated using Cockcroft-Gault formula at screening.

- h Includes laboratory assessments for troponin, BNP, CPK, and CK-MB which are to be collected on the same day as the echocardiogram. On Day -1 and at follow-up troponin, BNP, CPK, and CK-MB may be determined as part of the clinical chemistry panel. On Day 1, only troponin, BNP, CPK, and CK-MB will be collected at the sampling times specified in [Table 3](#).
- i Supine blood pressure and pulse rate will be evaluated after the subject has rested in the supine position for at least 10 minutes prior to the evaluation. If possible, the same arm and equipment should be used for each evaluation.
- j Vital signs will be recorded at predose and 1.5, 6, and 24 hours postdose.
- k A 12-lead dECG and vital signs will be performed after the subject has rested in a supine position for at least 10 minutes prior to the evaluation.

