3.2 Individual stopping criteria

The individual stopping criteria are:

- Any volunteer who experiences a 10% drop in LVEF from baseline taking the value to below 55% must be withdrawn from the study and referred to a cardiologist for management and monitoring.
- Any volunteer with an AE of dyspnea will be withdrawn from this study. The event must be fully investigated according to the AZD6244 dyspnea algorithm.
- Any volunteer experiencing a visual AE should have a full ophthalmological examination. If a retinal abnormality is identified, volunteers should be withdrawn and an OCT scan performed. All abnormalities should be followed up to resolution. The assessments will be repeated 28 days later to document resolution.
- In the event of a cardiac AE or a clinically significant increase in troponin and CK-MB at the 6 hour postdose time point, the volunteer should have an echocardiogram performed, a follow-up blood sample for troponin, BNP, CPK, and CK-MB taken.

The volunteer must be withdrawn from the study and referred to a cardiologist for management and monitoring.

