7.1 Volume of blood

The total volume of blood that will be drawn from each volunteer in this study is as follows:

Table 7 Volume of blood to be drawn from each subject

Assessment		Sample volume (mL)	No. of samples ^a	Total volume (mL) ^a
Safety	Clinical chemistry ^b	8.5	6	51
	Hematology	4	6	24
	Serology	8.5	1	8.5
Pharmacokinetic	AZD6244, N-desmethyl AZD6244, and AZD6244 amide	2	44	88
Cardiac biomarkers (troponin, CPK and CK-MB) ^c		5	9	45
Cardiac biomarker (BNP)		4	14	56
Optional pharmacogenetics		10	1	10
Discard ^d		1	44	44
Total				326.5

^a Blood samples based on all 4 treatment periods, as applicable.

^b On Day -1 (all 4 periods) and at follow-up, the cardiac biomarkers (troponin, CPK, CK-MB) will be determined as part of the clinical chemistry sample.

^c On the day of screening echocardiogram and on Day 1 (all 4 periods), the cardiac biomarkers (troponin, CPK, CK-MB) will be collected as a separate sample.

^d Discard volume calculated for each PK sample, in case an indwelling catheter is used.

The number of samples taken, as well as the volume required for each analysis, maybe changed during the study (ie, if additional samples are drawn for repeated safety assessments).

However, the maximum volume to be drawn from each healthy volunteer will not exceed 450 mL ie, the same volume as would be drawn during a regular blood donation.

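### The baseline rule takes the 6-hour change in troponin, BNP, CPK and CK-MB from Day -1, although a Day 1 predose sample is drawn in every period

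*Protocol*

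**What the plan says.** Section 11.1.1 defines change as the posttreatment value minus baseline and gives three baselines:

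- laboratory: "Clinical laboratory tests: Day -1 in corresponding treatment period"
- vital signs: "Vital signs: Day 1, predose in corresponding treatment period"
- digital ECG: "Digital ECG: Day 1, predose in corresponding treatment period"

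It adds a fallback: "If a volunteer is missing the baseline collection, the previous nonmissing evaluation will become the baseline value".

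Troponin, BNP, CPK and CK-MB are included in clinical chemistry in Sections 1.3.3, 6.2.1 and 6.2.2 and in the clinical chemistry column of Table 6. No separate baseline is given for them.

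Their sampling differs from the rest of the panel. Table 2 footnote h states: "On Day 1, only troponin, BNP, CPK, and CK-MB will be collected at the sampling times specified in" Table 3, which marks 0 h and 6 h. They are also taken on Day -1 of each period. For three of them, Table 7 footnote b says: "On Day -1 (all 4 periods) and at follow-up, the cardiac biomarkers (troponin, CPK, CK-MB) will be determined as part of the clinical chemistry sample".

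Section 12.2.4 summarizes absolute values and changes from baseline at scheduled assessments. It also says that safety data will be judged for significant change relative to predose.

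Section 3.2 makes a "clinically significant increase in troponin and CK-MB at the 6 hour postdose time point" one of the events that lead to an echocardiogram, repeat markers and withdrawal. It names no reference sample.

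**The concern.** By Table 2, the general laboratory panel is taken within a period only on Day -1. For those tests Day -1 is the only scheduled within-period baseline, and no in-period postdose change exists to be computed. The four cardiac markers are the exception: they have a scheduled postdose value and a predose value on the same day. For them the rule selects the more distant of two available predose samples.

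What is at stake is how the 6-hour change tables are read. A movement between the Day -1 draw and dosing cannot be caused by that period's dose, yet it enters the reported change in full. It could make the change look larger or smaller than what happened after dosing. The study lists decreased LVEF among its relevant risks (Section 1.3.2), so these tables will be read for cardiac safety.

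**Working it through.** **1. Is a 0 h sample really drawn in each period?** Table 7 can be reproduced from the schedule.

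- Separate troponin/CPK/CK-MB samples: 1 at screening + 4 periods × 2 Day 1 draws = 9. Table 7 states 9.
- BNP samples: 1 at screening + 4 on Day -1 + 4 × 2 on Day 1 + 1 at follow-up = 14. Table 7 states 14.
- Total volume: 51 + 24 + 8.5 + 88 + 45 + 56 + 10 + 44 = 326.5 mL. Table 7 states 326.5 mL.

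With only the 6 h draw on Day 1, the counts would be 1 + 4 = 5 and 1 + 4 + 4 + 1 = 10. The 0 h sample is therefore planned and counted in all four periods.

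**2. What does the planned change contain?** Write Y(-1), Y(0) and Y(6) for the Day -1, 0 h and 6 h values in one period:

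Y(6) − Y(-1) = [Y(6) − Y(0)] + [Y(0) − Y(-1)]

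The second bracket lies wholly before the dose. With the 0 h baseline it drops out.

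**3. How long is the extra interval?** The protocol gives no clock time for the Day -1 draw or the dose. Assume a draw between 08:00 and 22:00 and dosing between 07:00 and 10:00. The gap in hours from draw to dose is 24 − draw + dose.

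- Shortest: 24 − 22 + 7 = 9 h to dosing, and 9 + 6 = 15 h to the 6 h sample.
- Longest: 24 − 8 + 10 = 26 h to dosing, and 26 + 6 = 32 h to the 6 h sample.

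With the 0 h baseline, the span is 6 h plus at most the 60-minute predose window of Section 6, so about 6 to 7 h.

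**4. Can the drift be estimated from a control?** No. All six sequences in Table 5 consist of Treatments A, B and C, and each is AZD6244. One row label in Table 4 mentions placebo, but no sequence contains it.

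**5. Does the fallback rule rescue the 0 h value?** No, it looks backward. If Day -1 is missing in Period 1, the baseline becomes the screening value, which may date from as early as Day -28. In Periods 2 to 4, read literally, it becomes the last value of the preceding period, which by Table 3 is a 6-hour postdose value. In both cases a same-day 0 h sample would go unused.

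**6. Does it affect treatment comparisons?** If the mean of the second bracket is the same amount d in every period, each treatment's mean change is shifted by d, and the difference between two treatments is not shifted. Only drift that varies between periods or treatments would remain.

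**The case against.** The strongest reply is that little is lost. The 0 h values are listed and fall under the absolute-value summaries of Section 12.2.4, so a reader can see 0 h and 6 h side by side. The summaries are descriptive, with no test attached. Different baselines for different measures are not in themselves a contradiction. Table 2 and Table 7 also give the cardiac markers their own rows, so it can be argued that they are not clinical laboratory tests under Section 11.1.1. The first two arguments stand and limit the size of the point. The third is fair, but the predose wording in Section 12.2.4 still sits badly with a Day -1 baseline for markers that have a predose sample. The fourth would leave the markers with no baseline at all, which the same one-line change cures.

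Three stronger readings are tempting, and the protocol does not support them.

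- A reader might infer that the withdrawal criterion in Section 3.2 is computed from Day -1. That criterion is a judgment of clinical significance, and nothing ties it to Section 11.1.1.
- A reader might infer a drift of known size and direction, for example muscle-enzyme values falling with rest after admission. The protocol gives no figures for this. Section 5.1 bars strenuous activity from 72 hours before dosing, which weakens that mechanism for CPK and CK-MB and says nothing about troponin or BNP.
- A reader might infer bias because the Day -1 and Day 1 samples use different tubes. Section 6.3.5 sends the safety samples to one accredited laboratory, and nothing indicates a different assay.

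**Conclusion.** The point holds in a limited form. As written, the 6-hour change in the four cardiac markers is measured from Day -1, although a planned and counted 0 h sample is available in every period. The change therefore carries an unspecified pre-dosing interval, about 9 to 26 hours under the clock times assumed above, and there is no placebo period against which to judge it. A 0 h baseline would not remove all non-drug variation, since 6 to 7 hours would remain, but it removes the part that lies wholly before the dose.

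The conclusion rests on reading the markers as clinical laboratory tests, as Section 1.3.3 and Table 6 do. It does not rest on any assumed amount of drift, and no claim is made that a cardiac signal would in fact be hidden or created. Severity is minor to moderate: the effect is on descriptive safety change scores only, and the pharmacokinetic objectives are unaffected.

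**What to change.** In Section 11.1.1, add a baseline line for troponin, BNP, CPK and CK-MB: Day 1, 0 h, of the period concerned, falling back to Day -1 of the same period if the 0 h value is missing. Restrict the present Day -1 line to the remaining laboratory tests. Day -1 marker values stay in the listings and absolute summaries.

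Separately, the sponsor should state which sample the 6-hour increase in Section 3.2 is judged against and reconcile that wording with Section 11.1.1. Which reference to use there is a clinical decision and is not proposed here.

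The cost is a line or two of wording. The 0 h samples are already in the counts of 9 and 14 in Table 7, so no blood draw, visit or procedure is added.

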11.1.2 Other significant adverse events (OAE)

During the evaluation of the AE data, an AstraZeneca medically qualified expert will review the list of AEs that were not reported as SAEs and discontinuations due to AEs (DAEs). Based on the expert's judgment, significant AEs of particular clinical importance may, after consultation with the Global Patient Safety Physician, be considered other significant AEs (OAEs) and reported as such in the CSR. A similar review of laboratory/vital signs data will be performed for identification of OAEs.

Examples of these are marked hematological and other laboratory abnormalities, and certain events that lead to intervention (other than those already classified as serious), dose reduction, or significant additional treatment.

Any abnormal deviation in ECG intervals, amplitude, or morphology that is associated with symptoms is to be reported as an AE.

Any abnormal deviation in ECG/telemetry intervals, amplitudes, or morphology that is deemed to require a change in patient care, surveillance, or study participation is to be reported as an AE/DAE.

Any asymptomatic deviation in ECG/telemetry intervals, amplitudes, or morphology that is deemed not to constitute a safety concern for the individual volunteer, nor to require a change in volunteer care, surveillance, or study participation is to be reported qualitatively as an outlier value or with a narrative in the CSR. This includes also eg, short, asymptomatic, accidentally found paroxysmal supraventricular tachycardia or nonsustained ventricular tachycardia with characteristics that are normally not associated with test drug exposure:

Extra measurements (such as unscheduled or repeat assessments) will not be included in the descriptive statistics, but will be included in data listings. All AEs, ECG outliers for QTcF (ie, greater than 450, greater than 480, greater than 500 ms, or change from baseline greater than 30 and greater than 60 ms) and clinical laboratory outliers that occur following the first dose of IP will be included in the tabulations of AEs and outlier events, including episodes that occur at unscheduled evaluations or during the washout period between treatments.

